10.6. Study Initiation

Before the study drug can be shipped to the study site and before the study can begin, the following documents must be submitted and received by the Sponsor:

- Original US FDA Form 1572 signed by the investigator
- Documentation of the IRB approval of the protocol and Informed Consent
- A copy of the IRB-approved Informed Consent and HIPAA authorization that will be used
- Copy of current curriculum vitae and medical licenses of the investigator
- A membership list of the IRB
- Investigator's financial disclosure form

The Sponsor will notify the site when the study can begin.

10.7. Case Report Forms and Study Records

The investigator will comply with the requirements for all assessments and data collection for each subject, as specified in the protocol.

During each subject's visit to the clinic, the investigator or qualified designee will record progress notes in the subject's medical record to document all significant observations. At a minimum, these notes will contain the following:

- Documentation of the informed consent process, including any revised consents.
- The date of the visit and the corresponding visit or day in the study schedule.
- General subject status remarks, including any significant medical findings. The severity, frequency, and duration of any AEs and the investigator's assessment of relationship to study drug must also be recorded.
- Any changes in concomitant medications.
- A general reference to the procedures completed.
- The signature (or initials) and date of all clinicians who made an entry in the progress notes.

In addition, any contact with the subject via telephone or other means that provides significant clinical information will also be documented in the progress notes, as described above.

Data for this study will be captured in electronic eCRFs. Study auditing, data entry, verification and validation, and subsequent analysis will be performed by the Sponsor, or its designees, in accordance with GCPs and established Standard Operating Procedures.

Clinical data (including AEs, concomitant medications, and clinical laboratory data) will be entered into a database. The creation and validation of the database, data entry, validation, and verification will be performed according to 21 CFR and other applicable local regulations. The data system includes password protection and internal quality checks, such as automatic range checks, to identify data that appear inconsistent, incomplete, or inaccurate.

10.8. Study Monitoring

The Sponsor or designee will assign monitors who will perform on site monitoring as frequently as necessary and in accordance with ICH GCP.

Source documents and eCRFs will be reviewed at monitoring visits and any findings will be discussed with the investigational staff. The Sponsor expects that at monitoring visits study documents and staff will be available and a suitable space will be provided for review of the study documents. The monitor will meet with the investigator on a regular basis to provide feedback on the conduct of the study.

For Part B, another monitor who is unblinded to subject treatment assignment will perform on-site monitoring of the drug accountability records.

10.9. Access to Source Documentation

The study may be subject to audit by the Sponsor, its designee, or by regulatory authorities. If such an audit occurs, the investigator must agree to allow access to required subject records. The investigator should notify the Sponsor promptly of regulatory authority audits that are scheduled and must forward copies of any findings or audit reports to the Sponsor promptly.

By signing this protocol, the investigator grants permission to personnel from the Sponsor, its representatives, and appropriate regulatory authorities for on-site monitoring and review of all appropriate study documentation, as well as on-site review of the procedures employed in data collection, where clinically appropriate.

10.10. Study or Study Site Termination

The Sponsor may suspend or stop the study at all centers or at specific study centers due to (but not limited to) the discovery of an unexpected, serious, or unacceptable risk to the subjects enrolled in the study, a decision on the part of the Sponsor to suspend or discontinue development of the product, failure of the investigator to enroll subjects into the study at an acceptable rate, failure of the investigator to comply with regulatory authority or ICH Guidelines, or submission of knowingly false information.

The investigator should contact the Sponsor immediately if contacted by a regulatory agency about an inspection.

It is important that the investigator and relevant personnel are available during the possible audits or inspections and that sufficient time is devoted to the process.

10.14. Retention of Data

When the study is completed, the investigator must retain the essential documents for as long as needed to comply with regulatory guidelines and Sponsor requirements. The investigator will notify the Sponsor prior to moving or destroying any of the study documents. It is the responsibility of the Sponsor to inform the investigator/institution as to when these documents no longer need to be retained. The investigator should take measures to prevent any accidental or premature destruction of these documents.

10.15. Study Report and Publications

A clinical study report (CSR) will be prepared and provided to the regulatory agency(ies). The Sponsor will ensure that the report meets the standards set out in the ICH Guideline for Structure and Content of Clinical Study Reports (ICH E3). Note that an abbreviated report may be prepared in certain cases.

Investigators in this study may communicate, orally present, or publish in scientific journals or other scholarly media only after written consent has been obtained from the Sponsor.

The investigator will submit to the Sponsor any proposed publication or presentation along with the respective scientific journal or presentation forum at least 60 days before submission of the publication or presentation.

No such communication, presentation, or publication will include the Sponsor's confidential information (see [Section 10.5](#)).

The investigator will comply with the Sponsor's request to delete references to its confidential information (other than the study results) in any paper or presentation and agrees to withhold publication or presentation for an additional 60 days in order to obtain patent protection if deemed necessary.

Three horizontal black bars of decreasing length from top to bottom, positioned at the bottom of the slide.

[REDACTED]

A horizontal bar chart consisting of four solid black bars of increasing length from left to right. The bars are positioned against a white background with no visible grid or axes.

[REDACTED]

[REDACTED]

Four thick black horizontal bars are arranged vertically, with the bottom bar being shorter than the others.

[REDACTED]

[REDACTED]

[REDACTED]

[REDACTED]

[REDACTED]

2.1 Study Objectives

2.1.1 Primary Objectives

The primary objectives [REDACTED] are:

- Determine the safety and tolerability of intravenous (IV) dosing of EQ001 in subjects with newly diagnosed acute graft versus host disease (aGVHD)
- Determine optimal IV dose level(s) of EQ001 in subjects with newly diagnosed aGVHD

2.1.2 Secondary Objectives

The secondary objectives [REDACTED] are:

- To characterize the pharmacokinetics (PK) of EQ001 in subjects with newly diagnosed aGVHD

Statistical Analysis Plan

Sponsor Name: Equillium Inc.

Sponsor Protocol ID: EQ001-aGVHD-001

[figure not shown]
- To assess the clinical activity of EQ001 in subjects with newly diagnosed aGVHD

2.2 Study Design

Overall study design includes an open-label (Part A, Phase 1b) component and a double-blinded, placebo-controlled (Part B, Phase 2) component. A two-part study utilizing different designs was chosen to support the attainment of the objectives that are specific to each part of the study. Execution of Part B of the study will commence only after Part A has been completed and Part A data warrants. Description of the design features of Part A of the study follows.

Part A has been designed to explore the safety and tolerability of ascending dose levels of the IV administration of multiple doses of EQ001. An open-label design is supported by the availability of extensive safety and tolerability data on itolizumab, active ingredient of EQ001, for which to compare the open label safety data generated in this study. A cohort-based dose escalation design was chosen to rigorously evaluate, and conservatively escalate, IV doses of EQ001.

After informed consent has been obtained, all subjects will be screened for potential participation, and those meeting eligibility criteria will be offered participation in the study. The study will enroll subjects with an initial clinical diagnosis of aGVHD requiring systemic immunosuppressive treatment

Each subject will have 2 months of study treatment and ten (10) months of clinical follow up, for a total of twelve (12) months in the study. The follow-up period will consist of a 2-month Safety Follow Up period (through Day 169) and then an 8-month Long-Term Follow-Up period (through Day 337). Figure 1 shows the study timeline for Part A.

EQ001 will be administered every 14 days for two months (5 doses) at the following ascending dose levels:

- Cohort 1: 0.4 mg/kg

Statistical Analysis Plan

Sponsor Name: Equillium Inc.

Sponsor Protocol ID: EQ001-aGVHD-001

- Cohort 2: 0.8 mg/kg
- Cohort 3: 1.6 mg/kg
- Cohort 4: 2.4 mg/kg

Part A of the study will utilize a standard 3+3 dose escalation design until a dose is selected. Cohort enrollment will proceed in a sequential manner starting with the lowest dose cohort. Each dose cohort will enroll 3 to 6 adult subjects. Subject incidence of dose limiting toxicities (DLTs) during the initial 29 days of treatment (DLT window) will primarily guide dose escalation decisions.

Subjects will be considered evaluable for DLT assessment if they have received at least two doses of study drug and completed through Study Day 29 assessments or received at least one dose of study drug and had a DLT within the DLT window. During the DLT assessment window, subjects who do not complete the specified study procedures or withdraw from the study for reasons other than a DLT may be replaced. Replaced subjects will receive the same dose level and cohort assignment as the subject they are replacing.

Established Data and Safety Monitoring Committee (DSMC) will apply the following dose escalation rules based on the subject incidence of DLTs:

- If 0 of the 3 initial evaluable subjects experiences a DLT, then escalation may proceed to the next highest dose level.

[figure not shown]
Statistical Analysis Plan

Sponsor Name: Equillium Inc.

Sponsor Protocol ID: EQ001-aGVHD-001

- If 1 of the 3 initial evaluable subjects experiences a DLT, then 3 additional subjects will be enrolled at the same dose level for a total of up to 6 evaluable subjects.
 - If 1 out of the 6 subjects experience a DLT, then escalation may proceed to the next higher dose level.
 - If 2 or more out of the 6 subjects experience a DLT, escalation to the next dose level will not proceed, next lower dose level will enroll additional subjects for a total of 6 evaluable subjects.
- If 2 of the 3 initial evaluable subjects experience DLTs, escalation to the next dose level will not proceed, next lower dose level will enroll additional subjects for a total of 6 evaluable subjects.

Enrollment of the next higher dose cohort will not commence until all safety data from all subjects from prior cohorts and all available safety data from the current cohort through Study Day 29 have been reviewed by the DSMC and approval is granted for dose escalation.

3. Clinical Activity and Safety Variables for Part A

3.1 Clinical Activity Endpoints

- Response to therapy (Complete response [CR], Very Good Partial Response [VGPR], Partial response [PR], No response [NR], and Progressive disease [PD])
- Progression-free survival (PFS)

Statistical Analysis Plan

Sponsor Name: Equillium Inc.

Sponsor Protocol ID: EQ001-aGVHD-001

- aGVHD activity index (aGVHD-AI) and change from baseline
- Organ stages and change from baseline
- aGVHD overall clinical grade and change from baseline
- Overall survival (OS) – Time from first dose to death from any cause
- Relapse incidence and non-relapse mortality
- Corticosteroid usage
- Subjects who discontinued corticosteroids
- Disease status (disease relapse or chronic GVHD (cGVHD)) during long-term follow-up period

3.2 Safety Endpoints

Safety evaluations include adverse events (AEs), clinical laboratory, vital signs and ECG results and may also include changes in the subject's physical examination findings.

4. Analysis populations

4.1 Safety Population

Safety population consists of all subjects who receive any study medication. All data summaries except PK and PD data related summaries will use this population.

4.2 Evaluable Population

The evaluable population consists of all subject who receive at least 2 doses of study medication through Day 29. This population will be used in selected analyses of response, relapse, and survival.

[figure not shown]

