In addition, if at any time up to Study Day 169, a subject has an unscheduled study visit, all procedures that were conducted at the visit will be collected in the electronic case report form (eCRF) as an unscheduled visit. If a subject experiences disease progression or recurrence, the subject should complete an unscheduled visit that includes disease assessments and grading.

Safety and Long-Term Follow-Up:

All subjects who complete study drug dosing will be evaluated on Study Day 169 for disease progression assessments, aGVHD organ stages and overall clinical grading, aGVHD-AI, PK [REDACTED], ADA, and AE monitoring .Collection of concomitant medications may be required after Day 85 through Day 169, if requested by the Sponsor for any ongoing safety concerns related to study drug.

During the Long-Term Follow-Up period, the site will phone subjects on Study Days 253 and 337 to collect information on disease status (disease relapse or cGVHD), long-term survival, and safety (eg, recent hospitalization or SAEs).

Dose Modification and Dose Schedule Deviation:

In Part A, if a subject has a DLT during the DLT window (Study Days 1-29), study drug dosing will be discontinued for that subject. Subjects experiencing a DLT will be encouraged to remain in the study and complete the remaining visits; the subjects will not be replaced. If a subject terminates early for a reason other than a toxicity during the DLT window, the subject may be replaced.

In the event of a clinically significant AE that is not a DLT, study drug dosing may be temporarily withheld, and supportive therapy administered, as clinically indicated. If the toxicity resolves to baseline or Grade 1 prior to the next scheduled dose, dosing may be continued at the next scheduled dosing visit as follows, with agreement of the Sponsor and/or Medical Monitor:

- at the assigned dose (subjects in Part A or Part B) or
- at the next lower dose level evaluated in Part A (subjects in Part B only)

Data and Safety Monitoring Committee (DSMC), Dose-Limiting Toxicity, and Stopping Criteria:

A DSMC will review all available clinical and laboratory safety data at defined intervals during the conduct of each cohort in Part A and periodically during Part B of the study. The DSMC will make recommendations regarding the continuation, discontinuation, or modification of the study, cohort advancement (during Part A), and progression to Part B of the study.

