7. ADVERSE EVENTS

An AE is any unfavorable and unintended sign (including an abnormal laboratory finding), symptom, or disease or any worsening of a pre-existing condition temporally associated with the use of a study drug, whether or not related to the study drug. AEs that occur after the first dose of EQ001 or during the study treatment and safety follow-up periods will be documented on the AE eCRF. The investigator will assess the AE severity and relationship of the AE to study drug. The investigator will treat the subject as medically required.

Laboratory values that are outside the laboratory reference range should be reported as AEs only if considered clinically significant by the investigator.

From the time of obtaining informed consent through the first administration of study drug, all SAEs and nonserious AEs related to protocol mandated procedures will be recorded on the SAE/AE eCRF. All other untoward medical occurrences observed during screening, including exacerbation or changes in medical history, will be captured on the medical history eCRF. Details on recording and reporting AEs are provided below.

AEs will be collected through Study Day 169 for subjects who complete study drug through Day 57. AEs will be collected through Study Day 85 for subjects who discontinue study drug early. Recent hospitalizations and SAEs, if applicable, will be recorded at the Day 253 and 337 visits.

The investigator's clinical judgment should be used to determine whether a subject is to be withdrawn due to an AE. In the event the subject requests to withdraw from study-related treatment, the subject should be asked to return for all remaining study visits through Study Day 169. In the event a subject is withdrawn from study, an early-termination visit should be completed.

All subjects experiencing AEs while on study drug, including clinically significant abnormal laboratory values, whether or not associated with use of the study drug, must be monitored until the condition returns to normal, returns to the subject's baseline, until the investigator determines the AE has reached a stable outcome and is no longer clinically significant, or the subject is considered lost to follow up.

If consent has not been withdrawn, all deaths should be reported through Study Day 337, even if study drug has been discontinued.

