6.9.6 Overall Survival

Overall survival (OS) is defined as time from first dose to death from any cause. For subjects who are alive at the time of analysis, OS will be calculated as the time from first dose to last known alive date and will be considered as censored. OS in days will be calculated as:

$$(\text{Death date or censoring date} - \text{first dose date} + 1)$$

OS data will be summarized similar to PFS data.

In addition to the safety population, this analysis will also be conducted using the evaluable population, the safety population for subjects with ≤ 3 day of systemic steroid dosing prior to dosing of study medication, and the safety population for subjects with > 3 day of systemic steroid dosing prior to dosing of study medication.

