6.9.9 Disease Status

Number and percentage of subjects with a diagnosis of disease relapse (Yes/No) or cGVHD (Yes/No) as assessed at Study Days 253 and 337 will be presented by visit.

In addition to the safety population, this analysis will also be conducted using the evaluable population, the safety population for subjects with ≤ 3 day of systemic steroid dosing prior to dosing of study medication, and the safety population for subjects with > 3 day of systemic steroid dosing prior to dosing of study medication.

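### Overall survival counted from first dose is repeated in a population that must reach a second dose, so about 14 days of survival are guaranteed and deaths before dose 2 are removed

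*SAP*

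**What the plan says.** - **Membership (SAP 4.2).** "The evaluable population consists of all subject who receive at least 2 doses of study medication through Day 29". Its declared use is: "This population will be used in selected analyses of response, relapse, and survival".
- **OS clock (SAP 6.9.6).** "Overall survival (OS) is defined as time from first dose to death from any cause". OS is summarised in the same way as progression-free survival, that is, by Kaplan-Meier with median and quartiles.
- **Populations for OS (SAP 6.9.6).** "In addition to the safety population, this analysis will also be conducted using the evaluable population". The visible text gives no landmark, delayed entry or reset of time zero for this repeat. Parts of the SAP are redacted.
- **Disease status (SAP 6.9.9).** The number and percentage of subjects with "disease relapse (Yes/No) or cGVHD (Yes/No) as assessed at Study Days 253 and 337 will be presented by visit", again repeated in the evaluable population.
- **Dosing calendar (SAP 2.2; Protocol 5.3.1).** Five doses at 14-day intervals.
- **DLT in Part A (Protocol Synopsis, Dose Modification and Dose Schedule Deviation).** After a DLT in the window, "study drug dosing will be discontinued for that subject". The same paragraph encourages these subjects to stay in the study for the remaining visits.
- **Default population.** SAP 4.1 and Protocol 9.9 both name the safety population for Part A efficacy summaries.

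**The concern.** Who belongs to the evaluable population is settled by something that happens after first dose: the subject must be alive and still on treatment to receive a second one. The OS clock nevertheless starts at first dose. Nobody in this population can die before dose 2, so the Kaplan-Meier curve is flat at 100% over that interval by construction. Deaths that did occur in the interval are missing from both numerator and denominator.

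The repeat in SAP 6.9.6 therefore has the same definition and time origin as the safety-population analysis but a different meaning. It is survival given that dose 2 was reached, measured from a point before that condition was met. A reader comparing the two results could take the difference as information about the drug in adequately treated subjects, when part of it is an artefact of selection. Part A plans about 24 subjects in escalation cohorts of 3 to 6, so one excluded early death can move a percentage visibly.

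**Working it through.** The documents state no OS rate, early-loss rate or event count for this analysis, so there is no planned figure to reproduce. The survival and early-loss values below are assumptions.

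**1. Guaranteed time.** Dose days are 1 + 14(i − 1) for i = 1 to 5, which gives Days 1, 15, 29, 43 and 57. The last agrees with Protocol section 7: "AEs will be collected through Study Day 169 for subjects who complete study drug through Day 57". Dose 2 on Day 15 guarantees L = 15 − 1 = 14 days. If the wording of SAP 4.2 is read as requiring completion of Day 29, L = 29 − 1 = 28 days.

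**2. Bias under a constant hazard.** Day 337 is 336 days after first dose. Let S be 12-month OS in all dosed subjects, and suppose that the only subjects who miss dose 2 are those who die first. The evaluable figure is then S / S^(L/336).

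| Assumed S | L = 14: reads as | Bias, points | L = 28: reads as | Bias, points |
|---|---|---|---|---|
| 50% | 51.5% | 1.5 | 53.0% | 3.0 |
| 60% | 61.3% | 1.3 | 62.6% | 2.6 |
| 70% | 71.1% | 1.1 | 72.1% | 2.1 |
| 80% | 80.7% | 0.7 | 81.5% | 1.5 |

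**3. Bias if early deaths cluster.** Assume that 16 of 24 subjects survive (66.7%) and that k of the deaths fall before dose 2. The evaluable figure is 16/(24 − k).

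- k = 1: 16/23 = 69.6% (+2.9 points)
- k = 2: 16/22 = 72.7% (+6.1 points)
- k = 3: 16/21 = 76.2% (+9.5 points)

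In a cohort of 6 with 4 survivors, one such exclusion moves 4/6 = 66.7% to 4/5 = 80.0%.

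**4. The opposite direction.** A subject can have only one dose and survive, for example after withdrawing or after a DLT between doses 1 and 2. With 16 of 24 surviving:

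- Excluding one such survivor gives 15/23 = 65.2% (−1.4 points).
- Excluding one early death and one survivor gives 15/22 = 68.2% (+1.5 points).

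The net shift is upward only when survival among the excluded is lower than in the whole group.

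**5. Chance that the two populations differ.** If a proportion q of subjects miss dose 2, the chance of at least one exclusion is 1 − (1 − q)^N. For assumed q of 5–15%, this is 71–98% with N = 24 and 26–62% with N = 6.

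**6. Disease status.** SAP 6.9.9 is a Yes/No count at two fixed visits. It has no time origin, so steps 1 to 3 do not apply to it. What remains is that its denominator is chosen by a post-baseline event.

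**The case against.** The case for leaving this alone has real weight. The evaluable-population OS is supplementary: the safety-population OS is already planned and is the default. Part A is uncontrolled, no hypothesis test uses this result, and escalation rests on DLTs. With 24 subjects and OS of 66.7%, the binomial standard error is √(0.667 × 0.333 / 24) = 9.6 points, so a shift of one or two points is well inside sampling noise. All of that stands and limits the importance of the point. It does not remove it, because the guaranteed interval is systematic and both analyses use the same subjects.

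Four stronger readings are tempting, and the documents do not support them.

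- **That relapse also carries immortal time.** The analysis repeated in SAP 6.9.9 has no clock.
- **That the excluded subjects are simply those who died or had early toxicity, so the bias is always upward.** Fewer than two doses can also follow withdrawn consent, investigator or sponsor judgement, non-compliance (Protocol 3.2.2) or use of a prohibited therapy (Protocol 5.4.2). Subjects with a DLT are encouraged to remain in the study and may survive. Treating every dropped subject as an early death gives the worst case, for example 0.70/0.90 = 77.8% when 10% are dropped and true OS is 70%.
- **That DLTs after the first dose are lost, or that SAP 4.2 contradicts the DLT-evaluable rule in SAP 2.2.** DLTs are tabulated by cohort in the safety population and listed (SAP 6.10). The DLT-evaluable set keeps one-dose subjects with a DLT because it serves escalation; SAP 4.2 serves selected activity analyses.
- **That the two OS results will be shown together without any caveat.** Table and figure specifications are in a separate document that is not available here.

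**Conclusion.** The point holds for one supplementary analysis. OS in the evaluable population, as specified in the visible text, does not estimate survival from first dose, because survival to dose 2 is a condition of entry.

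Under a constant hazard and assumed 12-month OS of 50–80%, the upward bias is small: about 0.7–1.5 points, or 1.5–3.0 if 28 days are guaranteed. It becomes material if deaths cluster before dose 2, at +2.9 to +9.5 points for 1–3 such deaths among 24 subjects with 16 survivors. Surviving one-dose subjects offset it and could reverse the net shift. For disease status the issue is only a denominator selected after baseline. Dose escalation, the DLT tables and the safety-population OS are not affected. The change is still worth making because it costs almost nothing.

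**What to change.** - **OS (SAP 6.9.6).** State that the safety population is the only one in which OS is analysed from first dose. For the evaluable population, either drop OS or restart the clock, at dose 2 or at a Day 29 landmark that includes only subjects alive and in follow-up on that day. Label the result as conditional survival.
- **Membership (SAP 4.2).** Say whether a subject must complete Day 29 or only receive two doses by then. A clock started at dose 2 removes the guaranteed time only under the second reading; under the first, the Day 29 landmark is needed.
- **Disease status (SAP 6.9.9).** If the evaluable population is kept, label it as selected after baseline and report the number and outcomes of the excluded subjects.

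**Cost.** A few sentences in the SAP and a footnote, with no new data. The supplementary OS figure may look less favourable, and it will describe only subjects who reach the landmark. A Day 29 landmark also leaves deaths between dose 2 and Day 29 out of that display, although they remain in the safety-population analysis.
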